3.6.4.3 Investigation data exempt from blinding

For the purpose of **subject monitoring**, the CSCs and excluding all other investigators, will have access to the gaming-time and questionnaire-completion-status data of individual identifiable subjects. This information will be available to the CSCs for AE report, email, or

phone call interactions with the subjects so that the CSCs are able to make informed inferences, e.g., about the subject's study compliance. Notably, the CSCs will also have access to the suicidality-related questionnaire responses for subject monitoring as specified in [3.6.3.5](#). The CSCs remain blinded to all other investigation data, and especially the data about the study arm, game performance, and all other questionnaire replies of the subjects.

For the purpose of **study monitoring**, the investigators, excluding the CSCs, will have access to the gaming-time, questionnaire-completion-status, and study-arm data of individual but unidentifiable subjects. These data will enable the assessment of whether the criteria for the interim analysis or study completion are met.

- These data are needed because the interim analysis (see [3.7.5](#)) is triggered when each arm has 33 subjects that have completed the intervention (specifically, the 12 first weeks, which are follow-up for the TAU arm) and meet the inclusion criterion (see [3.7.2](#)) to data analysis.
- Conversely, termination of the investigation (see [3.7.4.2](#)) will be triggered when each arm has 133 subjects that have completed both the intervention and the follow-up period and meet the inclusion criterion (see [3.7.2](#)) to data analysis.

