- The effects of MEL-S01 on depressive symptoms as measured by PHQ-9 are mediated by positive game experience as measured by the immersive experiences questionnaire (IEQ).

Exploratory hypothesis

- The effects of the MEL-T01 and MEL-S01 on MDD symptoms are sustained in the follow-up period as measured by the change of PHQ-9 scores between T3 and T4.
- The effects of MEL-T01 and MEL-S01 will also emerge in the TAU group once as measured by the change of PHQ-9 between T3 and T4.
- The MEL-T01, MEL-S01, and TAU cohorts are equal in how they are treated for depression over the intervention period aside from the intervention.
- Interventions MEL-T01 and MEL-S01 are not significantly associated with an increase from T0 to T3 in game addiction as measured by the 7-item game addiction scale (GAS).
- The effects of the MEL-T01 and MEL-S01 on depressive symptoms as measured by PHQ-9 are (negatively) mediated by substance abuse as measured by ASSIST-LITE.
- The effects of MEL-T01 and MEL-S01 on depressive symptoms as measured by PHQ-9 are mediated by PTSD symptoms as measured by PTSD checklist for DSM-5 (PCL-5).
- The effects of MEL-T01 and MEL-S01 on depressive symptoms as measured by PHQ-9 are mediated by experiential avoidance as measured by the brief experiential avoidance questionnaire (BEAQ).

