3.6.3.3 Evaluation of inclusion and exclusion criteria

The subjects are presented in written form the exclusion and inclusion criteria in the recruitment phase (Appendix 1 - Recruitment notice) and in the information regarding the study (Appendix 2 - Participant information and consent form).

After the subject has signed up to the study and filled the first set of questionnaires (T0), the clinical subject coordinator (CSC) calls them via phone to confirm they meet the inclusion and do not meet the exclusion criteria (Appendix 5 - Clinical Subject Coordinator phone call). See section 3.6.5.2.

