3.7.1.2 Clinical questionnaires

The subjects fill questionnaires prior to the intervention (T0), and 4 (T1), 8 (T2), 12 (T3), and 24 (T4) weeks from the beginning of the research. All questionnaires are answered online.

The subject must fill the questionnaires at T0 before they are randomised into one of the three research arms: the intervention doesn't begin before the subject has filled the questionnaires. At T1, T2, T3 and T4, the subjects have two weeks to fill the questionnaire from the beginning of the time point. If the subject doesn't fill the questionnaire within one week, they are followed up with a phone call.

ASSIST-LITE, PCL-5, and BEAQ are filled only once at T0. The state of care questionnaire is filled in T1, T2, T3, and T4. IEQ measures game experience and is filled only after the subject has played the game. Other clinical questionnaires are filled at T0, T1, T2, T3, and T4. (see also Table 5).

The questionnaires include:

- Immersive experiences questionnaire (IEQ)
- Questionnaire regarding their state of care
- Patient health questionnaire (PHQ-9)
- Quick inventory of depressive symptomatology (QIDS-SR16)
- General anxiety disorder questionnaire (GAD-7)
- Positive valence systems scale (PVSS)
- The ruminative response scale (RRS)
- Alcohol, smoking and substance involvement screening test lite (ASSIST-LITE)
- PTSD checklist for DSM-5 (PCL-5)
- Brief experiential avoidance questionnaire (BEAQ)
- Sheehan disability scale (SDS)
- Well-being index (WHO-5)
- 7 item game addiction scale (GAS)

For details when the subjects are asked to fill the questionnaire, see table 5. For the questionnaire descriptions see 3.6.5.1, and for questionnaire content, see Appendix 7 - Data collected in the study.

Table 5: Clinical questionnaires

	Content	Sign up and background questionnaires	T0 Before playing	T1: T0 + 4 weeks	T2: T0 + 8 weeks	T3: T0 + 12 weeks	T4: T0 + 24 weeks
1	Immersive experiences questionnaire (IEQ)			MEL-T01 MEL-S01	MEL-T01 MEL-S01	MEL-T01 MEL-S01	TAU
2	Treatment status -questionnaire			x	x	x	x
3	Patient health questionnaire (PHQ-9)		x	x	x	x	x
4	Quick inventory of depressive symptomatology (self-report) (QIDS-SR16)		x	x	x	x	x
5	General anxiety disorder questionnaire (GAD-7)		x	x	x	x	x
6	Positive Valence Systems Scale (PVSS)		x	x	x	x	x
7	Short-version ruminative response scale (RRS)		x	x	x	x	x
8	Alcohol, Smoking and Substance Involvement Screening Test (ASSIST-LITE)		x				
9	PTSD Checklist for DSM-5 (PCL-5)		x				

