10	Brief experiential avoidance questionnaire (BEAQ)		x				
11	Sheehan disability scale (SDS)		x	x	x	x	x
12	The world health organisation -five well-being index (WHO-5)		x	x	x	x	x

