3.10.1 Subjects deviations or violations

The majority of human made deviations are mitigated because the majority of the intervention is digital: answering questionnaires as well as playing the game. Wherever possible, we have mitigated the possibility for the subject to deviate from the CIP.

Before the subject is included in the research, they complete the signup process (see 3.7.1.1), first set of clinical questionnaires (see 3.7.1.2), and their MDD diagnosis is confirmed through clinical interview (see 3.7.1.5). Only then the subject is randomised to MEL-T01, MEL-S01, or TAU group, and they are given access to the intervention (for groups MEL-T01 and MEL-S01). Thus we mitigate the risk of the subject not meeting the inclusion/exclusion criteria.

When the subject arrives at T1, T2, T3, and T4, they are emailed the instructions to complete clinical questionnaires. In addition, the reminder to complete the questionnaires is shown to the MEL-T01 and MEL-S01 group in the game, and they are not able to make progress until they have completed the questionnaires. The questionnaires are filled online. If the subject doesn't fill the questionnaires in 7 days from the onset of T1, T2, T3, or T4, they are followed up with a phone call by the CSC.

The subject is recommended to play the game for 48 hours during the 12 week play period. To be included in the sample we require 24 hours of gameplay. When the subject is contacted by the CSC, the CSC has access to the subject total game time and number of weeks played (but they do not know the subject group). If the subject total game time divided by the number of weeks played is less than 2 (the minimum required), the CSC kindly discusses the topic with the subject encouraging them towards reaching 24-48 hours of playing time during the 12 week play period.

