3.11 Accountability

3.11.1 Control of access to the device

Access to the software is only available as long as the digital key is valid. The digital key can be activated and deactivated remotely by the researchers. Only one install is possible with one digital key. Deactivated key prevents launching the software. The researchers can deactivate the subject's key if the subject doesn't follow the researchers instructions. Access to the game requires login to the distribution channel (Steam) and login to the game client itself.

Access to the MEL-T01 and MEL-S01 software is restricted to subjects who have completed the signup pipeline, T0 questionnaires, and gone through the clinical interview by the CSC. After this, the subjects are randomised to one of the three groups.

Whether in TAU, MEL-T01, MEL-S01 group, the access to the training is 12 weeks from the beginning of the intervention. For 2 weeks after the intervention has ended, the access to the training is denied from the user, but they can access the main menu through which they can complete the questionnaire T3 (groups MEL-T01 and MEL-S01) or T4 questionnaire (TAU group).

After the two weeks are over, the access to the software is denied, and the subject can uninstall it from their device. See Table 6 for a detailed outline of the access to the device.

Table 6: Access to the device

Access to the device											
Study arms	T0 (Before playing)	T1: T0 + 4 weeks	T2: T0 + 8 weeks	T3: T0 + 12 weeks	T3 + 2 weeks	T4: T0 + 24 weeks	T4 + 2 weeks.	After T4 + 2 weeks			
MEL-T01 intervention	T0 begins after CSC confirms the subject is eligible to the study. The subject is randomised to one of the three groups.	MEL-T01 intervention				Access to menu only.	No access to the device.				
MEL-S01 intervention		MEL-S01 intervention				Access to menu only.	No access to the device.				
Treatment as usual ("TAU")		Treatment as usual				Access to MEL-T01 or MEL-S01 intervention		Access to menu only.	No access to device.		

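### The T0 game-addiction answers are collected before the eligibility call but not used in it, so a subject who denies addiction by phone can be randomised with answers that would meet the plan's own interview cut-off (low severity, cheap to improve)

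*Combined protocol and SAP*

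**What the plan says.** **GAS at T0.** Section 3.7.1.2 lists GAS among the clinical questionnaires, names exceptions that do not include it, and continues: "Other clinical questionnaires are filled at T0, T1, T2, T3, and T4". An exploratory hypothesis in 3.5 concerns an "increase from T0 to T3 in game addiction as measured by the 7-item game addiction scale (GAS"), which requires a T0 score.

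**Order of steps.** Section 3.7.1.2: "The subject must fill the questionnaires at T0 before they are randomised into one of the three research arms". Section 3.6.3.3 says that once the subject has "filled the first set of questionnaires (T0), the clinical subject coordinator (CSC) calls them via phone to confirm they meet the inclusion" criteria and are clear of the exclusions. Section 3.10.1 lists sign-up, the first questionnaires and the interview, then: "Only then the subject is randomised to MEL-T01, MEL-S01, or TAU group". The body of 3.11.1 agrees: device access is "restricted to subjects who have completed the signup pipeline, T0 questionnaires, and gone through the clinical interview by the CSC".

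**The criterion.** Addiction to digital games is a self-reported exclusion (3.6.3.2). Under 3.6.5.2 the CSC asks about it by phone. Only a CSC who is unsure gives GAS as an interview. At least four items answered as sometimes or more often then excludes the subject, and the CSC may set a lower bar.

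**What the CSC sees.** Section 3.6.4.3 opens gaming time, completion status and suicidality replies, and closes with: "The CSCs remain blinded to all other investigation data, and especially the data about the study arm, game performance, and all other questionnaire replies".

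**The concern.** The trial gives a video game to people with depression, and the sponsor lists exclusion of addicted players as a precaution against game addiction (3.3.1.2; Table 2 in 3.3.1.6). Table 2 rates that risk as moderate in severity, probable before mitigation and possible after it.

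Whether the GAS cut-off is ever applied depends on the CSC becoming uncertain. The item most likely to create that uncertainty, the subject's own T0 answers, is on the server before the call and is not shown to the CSC. Subjects have also read the exclusion criteria beforehand (3.6.3.3), so the purpose of the direct phone question is plain to them. Seven frequency items would be a useful cross-check.

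What is at stake is how well one safety exclusion works. The PHQ-9 comparison, the alpha level and the sample size are not affected.

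**Working it through.** The plan gives no figure to reproduce. The check is mainly one of sequence and access.

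1. *Is GAS available before the call?* Yes, by 3.7.1.2 with 3.6.3.3. Table 5 as extracted has no GAS row: it ends at row 12, "The world health organisation -five well-being index (WHO-5"). Its 12 rows follow, in order, the first 12 of the 13 questionnaires listed in 3.7.1.2, and GAS is the 13th. A row lost in extraction is the likely explanation, and the hypothesis in 3.5 needs the T0 score in any case.
2. *Does anyone compare it with the cut-off before randomisation?* No section says so.
   - Section 3.6.4.3 does not open it to the CSC.
   - Section 3.6.3.5 says questionnaire answers are monitored, but the only action it specifies concerns suicidal ideation.
   - Section 3.8.2 describes edit checks, including for protocol violations, but as data validation. It mentions neither GAS nor a step before randomisation.
3. *Can a denier pass?* Yes. If the phone denial leaves the CSC in no doubt, 3.6.5.2 does not call for the GAS interview, and randomisation follows with every described step observed.

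**Scale.** The documents give no GAS distribution and no prevalence of game addiction, so the frequency cannot be estimated. As a conversion only: each 1% of the 800 planned subjects is 800 × 0.01 = 8. With 1:1:1 allocation, 8 × 2/3 = 5.3 would receive a game from T0 and 8 × 1/3 = 2.7 (the TAU arm) after T3. This does not give the number of extra interviews under the fix, because a flag would apply to everyone screened and that number is not stated.

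**Side effect of the fix on the GAS endpoint.** Assume a normal T0 score, T0-T3 correlation r, and exclusion of the top fraction p. The T0 mean falls by φ(z_p)/(1 − p) SD and the T3 mean by r times that, so the within-arm change rises by (1 − r) × φ(z_p)/(1 − p) SD.

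| p | φ(z_p)/(1 − p) | r = 0.5 | r = 0.8 |
|---|---|---|---|
| 1% | φ(2.326)/0.99 = 0.0269 | 0.0135 | 0.0054 |
| 5% | φ(1.645)/0.95 = 0.1086 | 0.054 | 0.022 |

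Both p and r are assumptions; the documents give neither.

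**The case against.** The strongest reply is that the plan never made the T0 GAS an eligibility instrument. The criterion is self-reported addiction, asked about by trained, licensed staff, with a scale as fallback. Suicidality (MINI Module B) and gambling (PGSI) are handled in the same way. The cut-off is defined only for GAS given as an interview. This stands, and it is why the point is an unused check and not an error.

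Second, the blinding sentence closes a paragraph about subject monitoring, so whether it was meant to govern screening is open. This also stands in part. The wording is general, though, and no other section gives the CSC the T0 GAS.

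Third, the call script is in Appendix 5, which is not in the file. If it requires GAS from everyone, the gap is closed. Sign-up also collects gaming history (3.7.1.1), and the documents do not say whether the CSC uses it.

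Fourth, the fix asks again, by phone, someone who has just denied addiction by phone. That limits its yield. It would still replace one transparent question with seven specific ones, and the CSC may apply a lower threshold.

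A reader might also infer that Table 6 in 3.11.1 contradicts the prose, because one cell has T0 begin after the CSC confirms eligibility. That cell can be read as the start of the 12-week clock, and the prose sections agree with one another. It merits at most an optional clarification.

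**Conclusion.** The point holds as a cheap improvement of low severity. On the prose, the T0 GAS precedes the call, the CSC is not given it, and the cut-off is used only on doubt. A subject can therefore be randomised with answers that would meet that cut-off.

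Stronger readings are tempting but unsupported:

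- *Ineligible subjects are admitted in breach of the protocol.* No stated rule is broken, since the cut-off does not apply to the self-completed form.
- *A T0 score at the cut-off shows addiction.* Both sources are self-report, and 3.6.5.1 says GAS only partly covers the gaming-disorder criteria. Such a score is a reason to ask further.
- *Many subjects are affected.* The frequency is unknown.
- *Subjects are left unprotected.* The phone question, the 90-minute daily lock-out, the CSC's view of game time, scheduled CSC calls, the end of access after 12 weeks and the ongoing treatment contact all remain.

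The conclusion assumes that Appendix 5 does not already require GAS from all. Any benefit also needs subjects still to be randomised. Planned completion was 31.12.2023, the current version is dated 26 February 2024, and recruitment status is not stated. If recruitment has closed, the benefit is zero.

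**What to change.** First check Appendix 5 and recruitment status. If GAS is not already required of everyone and randomisation continues, amend 3.6.4.3 and 3.6.5.2 as follows. The registration server scores the T0 GAS by the 3.6.5.2 threshold and shows the CSC a yes/no flag, not the answers, before randomisation. A positive flag requires the GAS interview that 3.6.5.2 already provides for. The existing cut-off and CSC discretion then decide eligibility.

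The cost is one scoring rule on data the server already holds (3.6.6.2), one item in the CSC's view and an amendment. Each flagged screened subject needs one extra seven-item interview (number unknown), and there will be a few more screen failures. Selection on baseline GAS could also raise the within-arm T0-T3 change by the small amounts in the table, in the direction the GAS hypothesis looks for. The rule acts before allocation, so comparisons between arms are preserved and the flag cannot reveal an arm.

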3.6.5 Clinical procedures and diagnostic methods

3.6.5.1 Questionnaires

We use the following questionnaires in gathering data about the subjects. For details regarding the questionnaires, see [3.7.1](#).

- Questionnaire regarding their state of care
- Patient health questionnaire (PHQ-9)
- Quick inventory of depressive symptomatology (QIDS-SR16)
- General anxiety disorder questionnaire (GAD-7)
- Positive valence systems scale (PVSS)
- The ruminative response scale short-version (RRS)
- Alcohol, smoking and substance involvement screening test lite (ASSIST-LITE)
- PTSD checklist for DSM-5 (PCL-5)
- Brief experiential avoidance questionnaire (BEAQ)
- Sheehan disability scale (SDS)
- Well-being index (WHO-5)
- 7 item game addiction scale (GAS)
- Problem gambling severity index (PGSI)

The immersive experiences questionnaire (IEQ, Jennett et al., 2008) measures the subjective experience of being immersed while playing a video game. It has 31 questions on a scale of 1-7, which require the subject to answer according to how they felt at the end of the game. One additional question - "How immersed did you feel?" - on a scale of 1-10, let's the researcher evaluate whether the IEQ reliably reflects the participant's immersive experience. Scores for five immersion factors can then be computed: challenge, control, real world dissociation, emotional involvement and cognitive involvement.

The questionnaire regarding state of care (Appendix 7) determines if there have been any changes in the subject's treatment during the preceding four weeks. If the subject reports changes to have occurred, they are then asked the same questions regarding treatment status as in the background questionnaire part 2: Mental health (see Appendix 7), excluding the open question regarding diagnoses.

The patient health questionnaire (PHQ-9, Kroenke et al., 2001) is a self-report measure of MDD and a component of the longer PRIME-MD diagnostic instrument for common mental disorders. The PHQ-9 scores each of the nine DSM-IV criteria for MDD from "0" (not at all) to "3" (nearly every day), providing a 0-27 severity score of depression.

The quick inventory of depressive symptomatology (QIDS-SR16, Rush et al., 2003) is a self-report measure derived from the 30-item Inventory of Depressive Symptomatology (IDS). It has 16 questions on a scale of 0-3 which assess the severity of depressive symptoms.

The general anxiety disorder questionnaire (GAD-7, Spitzer et al., 2006) is a 7-point screening tool for generalised anxiety disorder and its severity (scale 0-3).

The positive valence systems scale (PVSS, Khazanov et al., 2020) is a 21-item measure of the Positive Valence Systems domain of the National Institute of Mental Health's Research Domain Criteria. The scale (1-9) measures responses to a wide range of rewards: food, physical touch, outdoors, positive feedback, social interactions, hobbies, and goals. It is more strongly related to reward than punishment sensitivity, positive than negative affect, and depression than anxiety. Scores have been found to discriminate depressed from nondepressed individuals and predict anhedonia severity even when controlling for depression status.

The ruminative response scale (RRS) is a subscale of the response styles questionnaire (RSQ, Nolen-Hoeksema & Morrow, 1991). This study uses an 8-item short form of the RRS, which has been found to capture within-person variation in depressive brooding and reflection well (Brose et al., 2020).

The alcohol, smoking and substance involvement screening test lite (ASSIST-LITE, Ali et al., 2013) is a short-form screening tool of the original test (ASSIST), first developed for the World Health Organisation. The tool covers the misuse of and dependency on alcohol, tobacco, cannabis, stimulants, sedatives, opioids and other psychoactive substances including non-prescribed medicines. It is used to identify subjects whose alcohol and drug use and smoking may be increasing their risk of physical, psychological or social harm.

The PTSD checklist for DSM-5 (PCL-5, Weathers et al., 2013) is a 20-item self-report measure that assesses the 20 DSM-IV symptoms of PTSD. Subjects give their response on a 5-point scale according to how much they have been bothered by certain symptoms during the past month.

The brief experiential avoidance questionnaire (BEAQ, Gámez et al., 2014) is a short version of the multidimensional experiential avoidance questionnaire (MEAQ), which consists of 16 5-point Likert scale items. The BEAQ assesses experiential avoidance on six subscales: behavioural avoidance, distress aversion, procrastination, distraction and suppression, repression and denial, and distress endurance.

The Sheehan disability scale (SDS, Sheehan, 1983) is a brief measure of functional impairment. It is used to evaluate the impact of treatment on disability in a number of psychiatric disorders. The scale consists of five questions designed to assess the extent to which a subject's disorder or health problem interferes with their everyday life. The subscales of SDS - work disability, social life disability, family life disability - can be scored independently or combined as a score of global impairment.

The well-being index (WHO-5, WHO, 1998) is a brief measure of subjective psychological well-being. The index contains five positive statements which the subject rates from 0-5 according to how well the statements have applied to their life in the past two weeks. Raw scores are converted into percentages, with 0 reflecting the worst imaginable well-being and 100 the best imaginable well-being.

The 7-item game addiction scale (GAS, Lemmens et al., 2009) is a shortened version of the scale, which measures game addiction on seven criteria: salience, tolerance, mood modification, relapse, withdrawal, conflict and problems. GAS was developed before the publication of DSM-IV and partially covers the criteria of Internet gaming disorder (IGD). Subjects rate on a scale of 1-5 how often they have felt, thought or behaved a certain way in the last month.

Finally, the problem gambling severity index (PGSI) consists of nine of the 18 items from the Canadian problem gambling inventory (CPGI, Ferris & Wynne, 2001). It is a tool used for identifying and quantifying risk and problem gambling in the general population. Items are not focused on diagnostic criteria but rather assess gambling behaviour and the financial, social and health repercussions of gambling. The total score indicates non-problem gambling (0), low-risk gambling (1–2), moderate-risk gambling (3–7), or problem gambling (8+). Reports of lower levels of severity are to be interpreted cautiously (Miller et al., 2013; Samuelsson et al., 2019).

